### **III)** Data collection, management and analysis:

### **A] Data collection methods:**

to assess the primary and secondary outcomes, the principal investigator will take study models for every participant monthly during the follow up visits. Then will digitize the models and identify the landmarks, reference lines and planes on the pre, interim and post-retraction digital dental models for measurements reading. Also, by identifying the landmarks, reference lines and planes using CBCT taken before and after the completion of retraction.

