### **O** Diagnosis

The patient is checked to fulfil the previously mentioned inclusion criteria. Full set of records will be taken for every patient (study models, lateral cephalometric radiographs, and photos as part of the routine procedure for treatment of patients in the outpatient clinic of the Orthodontic Department, future University in Egypt.

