### **O** Clinical Procedure:

After taking pre-treatment records, every patient will receive:

- The third molars will be extracted surgically in the third molar extraction group four weeks before intervention commenced.
- Proper disinfection will be performed with a local disinfectant, BETADINE povidone-iodine 10%, at the area of mini-implant insertion.
- Two infra zygomatic mini-implants will be placed (Screw Tomas pin 10mm, dentaurum, Germany).
- Bands will be cemented to the upper first molars.
- The inner bow (1.2mm) is a modified version of the inner part of a conventional face bow. Two hooks were soldered onto the inner bow distal to the lateral incisor teeth regions. A U loop at the first premolar region and bends acting as a mesial stop will be bent in front of the maxillary first molars.

- The inner bow will be adjusted to the headgear tubes on the maxillary first molar bands, as the anterior component of the inner bow is 3 mm free from the labial surface of the anterior teeth.
- A distalization force of 300 gm/per side was applied to the maxillary molars via a closed coil spring (Tomascoil spring, Dentourum, Germany). According to the desired activation length, the distal end of the coil spring was set to the IZ mini-screw, while the mesial end was linked to the wire framework hook either directly or with a 0.01-inch stainless-steel ligature

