### 3) Methods of measuring of all outcomes:

Linear and angular measurements will be made on the pre, post and follow-up digital models and on the pre-and post distalization CBCT to assess the dental changes in intervention group.

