### **Participant timeline:**

1. The principal investigator will screen the potential patients through careful clinical examination of patients at the orthodontic department, Faculty of Oral and Dental Medicine, Future University in Egypt.

2. All recruited patients should fulfil the previously mentioned inclusion and exclusion criteria.

3. Every participant will be asked to sign an informed consent before the beginning of the study.

4. After patient's enrolment, each participant will be asked for preintervention records to ensure proper diagnosis.

[figure not shown]
5. The principal investigator will randomly allocate the patients to one of the intervention groups.

**6.** After patient's enrolment, pre-intervention records will be taken for each participant to ensure proper diagnosis (T0).

7. Every 4 weeks Each patient will have follow up visit, for appliance activation, uptake of impression for interim records and checking for mini-screws stability (T1-T7).

**8.** Post- records for each participant will be taken after duration of eight months (T8) at the same visit of appliance removal.

[figure not shown]
**9.** The principal investigator will continue the normal orthodontic treatment and achieved proper finished occlusion for every patient after the end of the study.

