### **D]Blinding:**

Because both the operator and the patient are aware of the clinical intervention, double-blinding is not feasible. However, the digital dental models and CBCT will be assessed blindly by a trained external assessor.

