### **C] Statistical Analysis:**

• The principal investigator will be responsible for the extraction of the required data from the CBCT taken before and after retraction as well as the study models taken at every follow up visit. The data will be sent to a specialized statistician.

• The specialized statistician will be responsible for the statistical analysis of the study by:

- 1. Presenting the data as mean, standard deviation (SD) and Standard error (SE) values.
- 2. Using Paired t-test to compare between the friction and the frictionless group of retraction as well as to compare between the pre-and post -treatment data for each group.

3. Using Anova test to determine the rate of anterior segment retraction.

4. Statistically evaluate the patient acceptance for both techniques.

• For this study, the specialized statistician will use IBM11 SPSS12 Statistics Version 20 for Windows to perform the required statistics.

• The significance level will be  $P \le 0.05$ . Highly significant variables are detected when P value is less than 0.01.

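### The plan promises a blinded external assessor but assigns landmark placement and data extraction to the principal investigator, who knows the arm, so it is unclear whether the primary outcome is measured blind

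*Combined protocol and SAP*

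**What the plan says.** Five sections bear on who measures the outcomes.

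- **Blinding:** operator and patient know the treatment, but "the digital dental models and CBCT will be assessed blindly by a trained external assessor".
- **Data collection methods:** the principal investigator takes the monthly study models. The next sentence has no subject of its own: "Then will digitize the models and identify the landmarks, reference lines and planes on the pre, interim and post-retraction digital dental models". A fragment on CBCT landmarking follows, again with no new actor.
- **Statistical Analysis:** "The principal investigator will be responsible for the extraction of the required data from the CBCT taken before and after retraction", and likewise from the study models.
- **Methods of measuring of all outcomes:** no reader is named. The section says only what is measured: "Linear and angular measurements will be made on the pre, post and follow-up digital models and on the pre-and post distalization CBCT".
- **Assessors Reliability:** trained examiners complete and repeat the measurements, and two assessors are compared. Blinding is not mentioned.

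On knowledge of the arm, the Participant timeline (item 5) states: "The principal investigator will randomly allocate the patients to one of the intervention groups".

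The outcome table lists both digital models and CBCT as instruments for the primary outcome, the anteroposterior movement of the upper first molars. It also lists third-molar tipping and third-molar vertical change (secondary outcomes 8 and 9) as CBCT readings.

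**The concern.** With operator and patient unblinded, blinded measurement is the only safeguard against detection bias that the plan states. The primary outcome is a distance, and the landmarks, lines and planes placed on each record largely determine it. A blinded person who reads a distance from landmarks set by someone who knows the arm is not making a blinded assessment. As the text stands, a reader cannot tell which procedure will be used.

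A second issue concerns CBCT. A scan taken after distalization shows whether third molars are present, so it can reveal the arm even to an external reader. The digital models are less exposed, because eligibility requires unerupted third molars and the tooth itself does not appear on a model.

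**Working it through.** **Step 1. Who does what.**

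| Task | Section | Person |
|---|---|---|
| Assess models and CBCT | Blinding | External assessor, blinded |
| Place landmarks, lines, planes | Data collection methods | Principal investigator (implied subject) |
| Extract data from CBCT and models | Statistical Analysis | Principal investigator (explicit) |
| Complete and repeat measurements | Assessors Reliability | Trained examiners, blinding not stated |
| Make linear and angular measurements | Methods of measuring of all outcomes | Nobody named |

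Only Data collection methods says who places the landmarks. No section says that the external assessor repeats that step, or that files are masked first. The coded IDs under Confidentiality are there to protect participants' identity.

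**Step 2. Does the principal investigator know the arm?** Yes, from timeline item 5. The Implementation section gives allocation to a main operator. The plan never says whether that is the same person, but the conclusion does not need it.

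**Step 3. When is the first CBCT taken?** Diagnosis says: "Full set of records will be taken for every patient (study models, lateral cephalometric radiographs, and photos". CBCT is not in that list. Clinical Procedure says: "The third molars will be extracted surgically in the third molar extraction group four weeks before intervention commenced". The sentence introducing that list places it after the pre-treatment records, and the timeline labels pre-intervention records T0. The text therefore leans towards a first scan before extraction, without saying so. The post-distalization scan comes after extraction in any case.

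**Step 4. The planning figures.** From the Sample size calculation:

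- Difference = 4.32 − 3.17 = 1.15 mm.
- Pooled SD = √((0.81² + 0.79²)/2) = 0.80 mm.
- Effect size = 1.15/0.80 = 1.437, as stated.
- A two-sided two-sample t-test at 5% with 80% power needs n = 8.68, so 9 per group, as stated.

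**Step 5. Illustration of what an unblinded reading could do.** The documents give no size for assessor bias, so every shift below is an assumption. Take a true difference of zero, a two-sided 5% two-sample t-test and n per arm. An arm-related shift b gives noncentrality (b/SD) × √(n/2) on 2n − 2 degrees of freedom. For example, b = 0.2, SD = 0.80 and n = 11 give 0.25 × √5.5 = 0.586 on 20 df (critical value 2.086), for a rejection rate of 0.086.

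| Assumed shift | SD 0.80, n = 9 / 11 | SD 2.15, n = 9 / 11 |
|---|---|---|
| 0.1 mm | 5.7% / 5.9% | 5.1% / 5.1% |
| 0.2 mm | 7.9% / 8.6% | 5.4% / 5.5% |
| 0.3 mm | 11.6% / 13.3% | 5.9% / 6.1% |
| 0.5 mm | 23.9% / 28.7% | 7.5% / 8.1% |

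The 0.80 mm SD comes from a pilot of three patients per group. The 2.15 mm SD is the one the Literature Review reports for bilateral distalization with the zygoma-gear appliance. The shift that doubles the error rate to 10% is 0.23–0.26 mm at SD 0.80 and 0.63–0.70 mm at SD 2.15. Statistical Analysis names a paired t-test between groups. The two-sample test is used here because the arms are parallel and it reproduces the planned sample size.

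**The case against.** **The investigator may only prepare the records.** Data collection methods says the landmarks are set so that measurements can then be read, which leaves room for someone else to read them. Data extraction, mentioned just before the data go to the statistician, may mean compiling readings. Assessors Reliability also describes examiners who measure. All of this is fair, and it makes the Statistical Analysis wording ambiguous rather than decisive. It does not rescue the landmarking step, where most of the judgement lies.

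**The wording looks carried over from another trial.** References to retraction and to friction groups suggest so. It is still the current instruction, and the only one that says who places landmarks.

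**The reliability checks would catch a problem.** Repeat readings, the ICC and the 1 mm disagreement rule compare examiners on the same record. They test agreement, and a bias shared by both examiners would pass. Nor are those examiners said to be blinded.

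**Masking could restore CBCT blinding.** Only in part. Hiding the third-molar region on every scan would make secondary outcomes 8 and 9 unreadable, so masking cannot be a general remedy.

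**A stronger reading is tempting.** A reader might infer that the primary outcome will definitely be measured unblinded, or that the result will be biased by a known amount. The documents support neither. The Blinding section still promises an external assessor, and no bias size is given. Nor do they show that the first CBCT reveals the arm, since the text leans towards a scan before extraction.

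**Conclusion.** The inconsistency is real and should be corrected. The plan promises blinded external assessment, yet assigns landmark and plane placement (by implied subject) and data extraction (explicitly, though the term is ambiguous) to a person who knows the allocation. No other section resolves this. If Data collection methods is followed, the primary outcome is not measured blind. If Blinding is meant to include landmarking, the plan does not say so.

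The conclusion rests on two premises: that the missing subject is the principal investigator, the only person named in that section, and that landmarks and planes largely determine the distance. It does not rest on the error rates, which range from negligible to substantial depending on the assumed shift and SD. Separately, post-distalization CBCT readings cannot be assumed blind whoever makes them.

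**What to change.** 1. **Name one measurer.** Reconcile Methods of measuring of all outcomes, Blinding, Data collection methods, Statistical Analysis and Assessors Reliability. The blinded external assessor should identify landmarks, lines and planes and make all readings. Any second examiner should also be blinded. Limit the principal investigator to impressions, scanning and records.
2. **Code the files.** Have someone who does not read them, such as the outside colleague under Data management, code models and scans to hide arm and, where feasible, visit. Withhold the key until readings are final. Align Access to data, which now admits only the supervisors and the principal investigator.
3. **Be explicit about CBCT.** State that the post-distalization scan shows whether third molars are present, so CBCT readings cannot be assumed blind. Treat the digital-model reading as the blinded measure of the primary outcome. Do not mask the third-molar region for outcomes 8 and 9. If masking is used for other CBCT readings, make the third-molar readings separately and afterwards on unmasked scans.
4. **State when the first CBCT is taken** relative to extraction.

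**Cost.** Rewording, coding effort and the assessor's landmarking and reading time. Single readings come to at most 22 × 9 = 198 models (T0–T8) and 22 × 2 = 44 CBCTs, fewer if patients finish early. Repeat readings for reliability, and any separate third-molar reading, are extra. The amount of distalization alone needs only the first and last model, 22 × 2 = 44. Sample size, visits and the list of outcomes are unchanged.

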#### **B]** Data management:

A colleague outside the research team will enter the data and organize it in excel sheets in the computer of the orthodontic department. Data will include all photographs, models, radiographs and filled questionnaire.

### **C] Statistical Analysis:**

• The principal investigator will be responsible for the extraction of the required data from the CBCT taken before and after retraction as well as the study models taken at every follow up visit. The data will be sent to a specialized statistician.

• The specialized statistician will be responsible for the statistical analysis of the study by:

- 1. Presenting the data as mean, standard deviation (SD) and Standard error (SE) values.
- 2. Using Paired t-test to compare between the friction and the frictionless group of retraction as well as to compare between the pre-and post -treatment data for each group.

3. Using Anova test to determine the rate of anterior segment retraction.

4. Statistically evaluate the patient acceptance for both techniques.

• For this study, the specialized statistician will use IBM11 SPSS12 Statistics Version 20 for Windows to perform the required statistics.

• The significance level will be  $P \le 0.05$ . Highly significant variables are detected when P value is less than 0.01.

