## Introduction

#### **Statement of the problem:**

Class II malocclusion is characterized by an incorrect relationship between the maxillary and mandibular arches due to skeletal or dental problems or a combination of both. The prevalence of this malocclusion was recently found to be 20.6% in the Egyptian population between 11 and 14 years  with mandibular retrusion as its most typical characteristic.

Non extraction Treatment of Class II malocclusions frequently requires distalization of maxillary molars into a Class I relationship by means of extraoral or intraoral forces. Several writers have studied the impact of the second molar eruption stage on the distalization of the first molar for many years. However, there is a paucity of research on the effects of third molar existence when distalization of the first molars.

In adults with erupted maxillary third molars, it is suggested to remove the third molars so that the extraction site may accommodate distalization and the regional acceleratory phenomena can aid in molar distalization. In contrast, adolescents often have unerupted third molars with partly developed roots the average age of third molar alveolar eruption is 20 years. Kinzinger et al. suggested a germectomy of the third molars prior to distalization using a pendulum appliance in young children in order to accomplish physical distalization of the molars. However, surgical extraction of adolescents' unerupted third molars may be challenging and unpleasant. To our knowledge, no research has assessed the impact unerupted third maxillary molars on distalization.

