# **B-Research question:**

Does extraction of the upper third molars have a different impact than nonextraction on distalizing maxillary first molars in Class II adolescents?

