### **Objectives of the study research**

### **Research hypothesis:**

The null hypothesis was that the presence and extraction of unerupted maxillary third molars would have a similar effect on the distalization amount of maxillary first molars and the other dental changes.

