### **E]** Sample size calculation:

The sample size calculation is based on the findings of a pilot study, including three patients from each group, in which the upper first molar distalization amount was the primary outcome. The mean (standard deviation) values were 3.17(0.81) mm and 4.32 (0.79) mm in the TMP and TME groups, respectively. The effect size was 1. 437. With alpha level of 0.05 and a test power of 80%, the minimum estimated sample size was 18 patients (9 patients per group). Considering drop out a sample size of 11 per group is appropriate.

Sample size calculation is performed Using G\*Power version 3.1.9.2.

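### The plan judges the arms by P ≤ 0.05 alone against a null of similar effect, with no arm difference, confidence interval or margin, so a non-significant result could be read as similarity that the data do not establish

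*Combined protocol and SAP*

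**What the plan says.** The Research hypothesis section states: "The null hypothesis was that the presence and extraction of unerupted maxillary third molars would have a similar effect on the distalization amount". The same sentence extends this null to the other dental changes. The research question, by contrast, is about a difference: "Does extraction of the upper third molars have a different impact than nonextraction on distalizing maxillary first molars in Class II adolescents".

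Under C] Statistical Analysis, the first item is "Presenting the data as mean, standard deviation (SD) and Standard error (SE) values". The second is "Using Paired t-test to compare between the friction and the frictionless group of retraction", and the same test is also used for before-and-after comparisons within each group. The significance level is P ≤ 0.05, with a further label: "Highly significant variables are detected when P value is less than 0.01".

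The sample size section plans for a difference only: "The mean (standard deviation) values were 3.17(0.81) mm and 4.32 (0.79) mm in the TMP and TME groups, respectively", followed by "With alpha level of 0.05 and a test power of 80" per cent. This gives 9 patients per group, raised to 11 for drop-out.

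No section plans an estimate of the between-arm difference or a confidence interval. None gives an equivalence margin or a smallest important difference, and none says how a non-significant result will be interpreted.

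**The concern.** A null worded as similarity, judged only by a P value, invites the conclusion that the two approaches are similar whenever P exceeds 0.05. Failing to reject is not evidence of similarity, least of all with 9 to 11 patients per arm. The difference in mm with its interval would show a reader how much remains possible, and the plan does not commit to reporting it.

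The point has practical weight. The Statement of the problem says that surgical extraction of adolescents' "unerupted third molars may be challenging and unpleasant". The literature review cites one study that recommends germectomy before distalization and another that suggests it may be avoidable in the short term. A statement that extraction and non-extraction are similar would bear directly on that disagreement. The null also covers all the secondary dental changes, for which no power is calculated.

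**Working it through.** **Inputs.** From the sample size section: pilot means 3.17 and 4.32 mm, SDs 0.81 and 0.79 mm, alpha 0.05, power 80%, 9 per group before drop-out and 11 after. From the Study design section: two parallel arms, 1:1. Two assumptions are added: an independent-groups t-test with equal variances (the plan names a paired test, which does not fit parallel arms), and two-sided testing (sidedness is not stated, but two-sided reproduces the plan's figure).

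**1. The plan's own figure.**
- Difference = 4.32 − 3.17 = 1.15 mm.
- Pooled SD = √((0.81² + 0.79²)/2) = 0.80 mm.
- Effect size = 1.15/0.80006 = 1.437, as stated.
- Power from the noncentral t distribution is 76.2% with 8 per group and 81.6% with 9. The minimum is therefore 9 per group (18 in all), as stated.

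**2. Width of the interval the plan does not ask for.** Half-width = t(0.975, 2n − 2) × SD × √(2/n).
- n = 9: 2.120 × 0.80 × √(2/9) = 2.120 × 0.377 = 0.80 mm.
- n = 11: 2.086 × 0.80 × √(2/11) = 2.086 × 0.341 = 0.71 mm.

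**3. What a just non-significant result leaves open.** At the boundary the observed difference equals the half-width, so the interval runs from 0 to twice the half-width:
- n = 9: 0 to 1.60 mm.
- n = 11: 0 to 1.42 mm.

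Both upper limits exceed the planned 1.15 mm.

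**4. Chance of P > 0.05 when a difference exists.** Noncentral t with noncentrality = true difference/(0.80 × √(2/n)).

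| True difference | 9 per arm | 11 per arm |
|---|---|---|
| 1.15 mm (planned) | 18% | 11% |
| 0.8 mm (illustrative) | 49% | 39% |
| 0.575 mm (half the planned effect, illustrative) | 70% | 64% |

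The last two rows are illustrative because the documents name no smallest important difference.

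**5. What a claim of similarity would need.** The table gives the power of two one-sided tests at 5% each, with true difference zero and SD 0.80 mm, over an assumed range of margins.

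| Margin | Power, 9 per arm | Power, 11 per arm | n per arm for 80% |
|---|---|---|---|
| 0.575 mm | 4% | 8% | 34 |
| 0.75 mm | 23% | 37% | 21 |
| 1.0 mm | 63% | 76% | 12 |
| 1.15 mm | 80% | 89% | 10 |

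**6. Sensitivity to the SD.** The pilot SD rests on three patients per group (4 degrees of freedom), and its 95% confidence interval is about 0.48 to 2.30 mm. The literature review reports 4.37 ± 2.15 mm for a zygoma-gear appliance in a single-group cephalometric study. If that ± figure is an SD and applied here, the half-width would be 2.15 mm (9 per arm) or 1.91 mm (11 per arm).

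**The case against.** The strongest reply is that the misreading is nowhere in the documents. No section says that P > 0.05 will be taken as similarity. The research question asks about a difference and the trial is sized to detect one, so the null may simply be an ordinary null, loosely worded. This stands: the text supports *could be read as* similarity, and no more.

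Four further limits also stand.
- A reader might infer that the trial cannot show similarity at all. That depends on the margin. At the planning SD and a true difference of zero, it could exclude 1.15 mm with 80% to 89% power. But 1.15 mm is the whole effect it was built to detect, and at 0.75 mm or less the power is at most 37%.
- A reader might infer that the Introduction asks whether surgery can be avoided. It does not. It calls extraction difficult for adolescents, reports a recommendation for germectomy, and says that the effect of unerupted third molars has not been assessed.
- A reader might infer that a false null result is likely even at the planned effect. At 1.15 mm the chance is 18% or 11%. The higher rates belong to smaller differences that no section calls important.
- Arm means and SDs are planned, so a reader could derive the difference and, for independent arms, its interval. No data are lost. What is missing is the commitment to report them.

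None of this supplies the missing estimate, interval or margin.

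**Conclusion.** The point holds as a gap in reporting and interpretation. The plan judges the arms by a P value alone, words its null as similarity without defining it, and commits to no between-arm estimate or interval. A just non-significant result would be compatible with a difference of about 1.6 mm (9 per arm) or 1.4 mm (11 per arm), against 1.15 mm planned.

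These figures rest on the pilot SD of 0.80 mm and on an independent-groups t-test. A larger SD would widen the interval. The documents do not show that the investigators intend to conclude similarity from a null result. They show only that nothing in the plan prevents it. The change should be made, because it decides what a null result may say and costs almost nothing.

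**What to change.** 1. In C] Statistical Analysis, make the primary result the between-arm mean difference in first-molar distalization (extraction minus non-extraction, in mm) with a two-sided 95% confidence interval from an independent-groups analysis. This replaces the paired test between arms and its friction and frictionless labels. An interval taken from a paired test would not be valid for these parallel arms.
2. Report the same for every secondary outcome measured in both arms. Third-molar outcomes exist only in the non-extraction arm and are left out.
3. In the Research hypothesis section, word the null as no difference in mean distalization.
4. State that P > 0.05 will be reported as no difference demonstrated, with the confidence limits given. It will not be reported as similarity unless the whole interval lies inside a margin fixed, with reasons, before the measurements are read. If no margin is agreed, the word similar should not be used.

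The cost is wording in two sections. SPSS prints the interval with an independent-samples t-test, and reporting it needs no extra patients. The small downside is a more cautious conclusion after a null result. If the investigators want to claim similarity within a narrow margin, the trial would have to be re-sized (for example, 21 per arm for an assumed margin of 0.75 mm at SD 0.80 mm).

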# Intervention:

Distalization of maxillary first molars using infra-zygomatic gear distalizer after extraction of maxillary third molars.

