# **Comparator:**

Distalization of maxillary first molars using infra-zygomatic mini-implants as anchorage unit without extraction of maxillary third molars.

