#### Study design

This research was a single-cantered, 2-arm parallel group randomized controlled clinical trial 1:1 allocation ratio, performed following the Consolidated Standards of Reporting Trials guidelines.

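### The only between-group test named is a paired t-test of arms that this trial does not have, so the primary comparison has no valid pre-specified test

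*Combined protocol and SAP*

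**What the plan says.** The Research hypothesis section sets a between-arm null: that "the presence and extraction of unerupted maxillary third molars would have a similar effect on the distalization amount of maxillary first molars" and on the other dental changes. Study design describes a "2-arm parallel group randomized controlled clinical trial 1:1 allocation ratio". The arms are "Distalization of maxillary first molars using infra-zygomatic gear distalizer after extraction of maxillary third molars" (Intervention) and distalization with infra-zygomatic mini-implants "as anchorage unit without extraction of maxillary third molars" (Comparator). Under Sequence generation, single patients are ordered by sorted random numbers, and under Implementation each patient is allocated to extraction or non-extraction. No section describes matching, crossover or a split-mouth design.

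The Statistical Analysis section then lists:

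- Item 2: "Using Paired t-test to compare between the friction and the frictionless group of retraction", and in the same sentence "as well as to compare between the pre-and post -treatment data for each group".
- Item 3: "Using Anova test to determine the rate of anterior segment retraction".
- Item 4: "Statistically evaluate the patient acceptance for both techniques".

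Item 2 names no outcome. No independent-samples test is named for the primary outcome anywhere in the document.

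**The concern.** A paired t-test analyses within-pair differences, so it needs a defined partner for each observation. Here the two arms contain different, unlinked patients. Right and left molars of one patient are paired within that patient, not across arms, so they do not supply the missing pairs.

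Item 2 can be read in two ways. Either it applies an unsuitable test to the extraction versus non-extraction comparison, or, because it names other arms, it specifies no test for that comparison. Under both readings the statistician must choose the primary test outside the plan or follow an instruction that does not fit the design.

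Following it literally has four effects:

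- the p-value depends on how patients happen to be paired;
- patients without a partner are dropped when the arms end up unequal;
- the error degrees of freedom halve;
- the confidence interval widens.

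The second half of item 2, pre versus post within each arm, is a correct use of the paired test and is not in question.

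**Working it through.** **Inputs** (Sample size calculation): mean (SD) 3.17 (0.81) mm with third molars present and 4.32 (0.79) mm with third molars extracted; effect size 1.437; alpha 0.05; power 80%; 9 per group, raised to 11 for dropout. No test, sidedness or dropout rate is stated.

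**1. Effect size.** Pooled SD = √((0.81² + 0.79²)/2) = 0.800. d = (4.32 − 3.17)/0.800 = 1.437, as stated.

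**2. Which test gives 9 per group?** Power is from the noncentral t distribution. For the independent test, df = 2n − 2 and noncentrality = d√(n/2). For the paired test, df = n − 1 and noncentrality = dz√n, with dz = d/√(2(1 − ρ)) for within-pair correlation ρ.

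| Test | Power just below 80% | First n with at least 80% |
|---|---|---|
| Independent, two-sided | 76.2% at 8 | **9 per group** (81.6%) |
| Independent, one-sided | 74.9% at 6 | 7 per group (81.3%) |
| Paired, two-sided, dz = 1.437 (ρ = 0.5) | 67.6% at 5 | 6 pairs (80.1%) |
| Paired, two-sided, ρ = 0 (dz = 1.437/√2 = 1.016) | 76.1% at 9 | 10 pairs (81.5%) |

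The paired test gives 9 pairs only if ρ is assumed to be about 0.10 to 0.22. The plan states no correlation. The two-sided independent test gives 9 with no added assumption.

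**3. Power if unrelated patients are paired arbitrarily (ρ = 0), two-sided 0.05.** At equal arm sizes the noncentrality is the same for both tests. The loss comes from the degrees of freedom (20 to 10 at 11 per group, 16 to 8 at 9).

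| Completers per group | Independent | Arbitrarily paired |
|---|---|---|
| 11 | 89.3% | 85.9% |
| 10 | 86.0% | 81.5% |
| 9 | 81.6% | 76.1% |
| 8 | 76.2% | 69.5% |

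With unequal completers, pairing keeps only the smaller number. These splits are assumed:

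- 11 and 10: 87.7% against 81.5%
- 10 and 9: 83.8% against 76.1%
- 11 and 9: 85.6% against 76.1%

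**4. Half-width of the 95% confidence interval** = t × 0.800 × √(2/n).

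- n = 9: independent 2.120 × 0.800 × √(2/9) = 0.80 mm; paired 2.306 × 0.800 × √(2/9) = 0.87 mm (ratio 1.088).
- n = 11: independent 2.086 × 0.800 × √(2/11) = 0.71 mm; paired 2.228 × 0.800 × √(2/11) = 0.76 mm (ratio 1.068).

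**5. Dependence on pairing order.** The simulation used the plan's own effect, with 3,000 data sets and 200 random pairings of each. Pairings fell on both sides of p = 0.05 in 45% of data sets at 9 per group and 32% at 11. On average 8.6% and 5.8% of pairings fell on the minority side.

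**6. Type I error.** In 40,000 null data sets with the pairing fixed in advance, rejection was 5.0% at 9 per group and 5.1% at 11.

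**The case against.** The strongest reply is that this is wording carried over from another study, that a competent statistician would use the right test anyway, and that literal use would do little harm. Type I error holds, paired power is still 85.9% at the planned 11 per group and 81.5% at 10, and most pairings agree. The 45% figure needs only one dissenting pairing in 200, so the 8.6% average is the fairer measure. All of this stands as to size. The power and interval figures also apply only if item 2 is read as pairing extraction with non-extraction patients. If it is read as naming no test for them, the gap is simply a missing test.

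Two narrower objections also have weight. A one-way ANOVA of two arms is equivalent to the pooled independent t-test, and item 3 does name ANOVA. However, item 3 ties it to the rate of anterior segment retraction, which is not an outcome of this trial, and does not describe it as an arm comparison. The mismatch with the sample size is an inference, because that section names no test; it is supporting evidence, and the stated sample size is not itself wrong.

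None of this supplies a valid test for the primary outcome. Carried-over text explains the error, and a choice made later by the statistician is what pre-specification is meant to avoid.

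**Conclusion.** The concern holds and must be fixed. The only between-group test named is unsuited to a parallel trial of unmatched patients and refers to arms that do not exist here, so the primary hypothesis has no valid pre-specified test. That is the ground for the severity.

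Literal use would cost about 3 percentage points of power at 11 per group (89.3 − 85.9 = 3.4) and about 5 to 6 at 9 (81.6 − 76.1 = 5.5). It would widen the interval by 7% to 9% and make the result depend on patient order. These figures assume the plan's pilot means and SDs, a two-sided 0.05 level and zero correlation between arbitrarily paired patients. Type I error is not inflated if the pairing is fixed without looking at outcomes.

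**What to change.** In Statistical Analysis:

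1. **Item 2, between arms.** Replace with wording such as: the extraction and non-extraction arms will be compared on first-molar anteroposterior change, one value per patient, by a two-sided independent-samples t-test, reporting the mean difference with its 95% confidence interval. State which measurement supplies that value, since the outcome table lists both digital models and CBCT for the primary outcome, and how right and left molars are combined.
2. **Item 2, within arms.** Keep the paired t-test for pre/post change only.
3. **Arm labels.** Use extraction and non-extraction here and in Sequence generation, which currently names en-masse and two-step groups. Correct the references to retraction in Data collection methods and in the Harm paragraph.
4. **Item 3.** Replace anterior segment retraction with the listed outcome, first-molar distalization rate, and name its between-arm test. First reconcile the criteria for ending distalization (Class I relation or eight months) with Participant timeline item 8 (post-records and appliance removal at eight months for each participant), so that the time denominator is defined. For example, 4.32 mm is 4.32/8 = 0.54 mm/month over eight months but 4.32/6 = 0.72 if distalization ended at an assumed six months.
5. **Item 4.** Patient acceptance is in neither outcome list. Either add it as an outcome with a stated analysis or remove it.

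Items 1 to 3 need no new data, software or patients; item 1 also needs a decision on the measurement source and on combining sides. The independent test at 9 per group has 81.6% power and at 11 has 89.3%, so the sample size stands. Item 4 depends on the reconciliation described, and item 5 needs a decision by the investigators.
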